During liver transplant procedure and immediately after finalization of venous, arterial and biliary anastomoses, a second biopsy will be obtained (formaldehyde). This biopsy is taken routinely as part or the liver transplant protocol at UAMS to address quality of the implanted allograft including damage from reperfusion. The allograft site from which biopsy will be obtained will be left to the discretion of the transplant surgeon, although it should be documented in the operative note.

Before transplantation, the following data will be collected about the donor (data will be collected from the United Network for Organ Sharing [UNOS] portal, which compiles deidentified clinical data relevant to liver transplantation):

- height,
- weight,
- gender,
- age,
- ethnicity,
- cause of death,
- comorbidities,
- platelets,
- bilirubin,
- ALP,
- ALT and AST on the day of TE,
- peak ALT and AST,
- presence of any infectious disease
- degree of steatosis from snap frozen biopsy
- NPO status will be documented as well (in hours), from last oral intake or stopping of enteral nutrition to TE procedure,
- Cold and warm ischemia will be documented as part of the standard of care

On the day of transplantation, the following will be recorded from the transplant recipients:

• Routine labs on the day of transplantation (CBC, chemistry, liver panel, INR).

After transplantation, the following liver transplant outcomes will be prospectively documented:

• development of primary non-function (PNF),

Study Title: Usefulness of Controlled Attenuation Parameter (CAP) for the assessment of liver steatosis in liver donors

PI: [name], MSc, DSc

Institution: University of Arkansas for Medical Sciences

- early allograft dysfunction (EAD),
- peak ALT,
- ICU length of stay,
- retransplantation, and
- death.

PNF will be defined as AST>3000, plus INR ≥2.5 or arterial pH ≤7.30 within 7 days from implantation; whereas EAD as total bilirubin >10 mg/dL on day 7, INR ≥1.6 on day 7, and ALT or AST >2000 U/L during first week post-LT. Need for retransplantation or death at 3- to 6- months post-transplant (depending on follow up protocol at each participating center) will be recorded as well. Where available, a follow up TE with Fibroscan 502 or 530 will be performed at a standard-of-care follow outpatient visit at 3-6 months post-transplant. The patient will lie over his/her back and both the M and XL probes will be used following the same steps described above.

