The first secondary aim is to examine correlation between TE results and fibrosis stage (Spearman's rho). In addition to correlating the TE results with fibrosis stage, we will explore whether the combination of CAP and TE results can define unacceptability and subsequently help in the decision to discard and organ. To achieve this goal a sensitivity analysis with various combinations of CAP and TE will be tested in logistic regression models, and then cut-off valued determined by constructing AUROC. Agreement between pathologist for both steatosis and fibrosis will be examined with the kappa statistic. A sensitivity analysis for donors on vasoactive amines or a peak ALT or AST >300 before procurement is planned to better determine accuracy of CAP/TE in liver donors.

The second secondary aim is to correlate CAP and TE results with various post-LT outcomes. Various (logistic, linear or proportional hazards) regression analyses will be used depending on the outcome variable of interest (PNF, EAD, retransplantation or death). Predictor variables will include CAP and TE as well as well-known donor and recipient predictors of LT outcomes (i.e. age, MELD, ICU-stay, etc).

The third secondary aim is to determine the change in CAP after LT. Baseline and follow up CAP determinations will be compared with paired t-test or Wilcoxon, depending on distribution of data. Normal distribution will be tested with Shapiro-Wilk. Categorical changes (i.e. \geq 34% to <34%) will be addressed with McNemar's test.

Accurate sample size determination is difficult in this pilot study because the test characteristics are not defined. We propose to examine as many donors as needed to achieve 100 transplanted liver allografts, which will allow detection of meaningful differences between livers with high versus low CAP values. If the prevalence of unacceptably high CAP value is as low as 5% of the livers, the sample size will permit detection of a threshold that has 80% positive predictive value or higher. Between the two participating institutions, it is expected to complete inclusion of 100 transplanted liver allografts in one year. It is expected to include no more than 60 patients at UAMS.

Data Collection and Handling

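### The outcome regressions put CAP, TE and an open-ended covariate list into 100 recipients with no sparse-data method; penalised fitting would remove most of the resulting bias

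*Combined protocol and SAP*

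**What the plan says.** The Data Analysis section gives the second secondary aim one short paragraph. On method: "Various (logistic, linear or proportional hazards) regression analyses will be used depending on the outcome variable of interest", followed by PNF, EAD, retransplantation and death, all of them binary or time-to-event. On covariates: "Predictor variables will include CAP and TE as well as well-known donor and recipient predictors of LT outcomes (i.e. age, MELD, ICU-stay, etc"). That is at least five terms, with the list left open.

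On size, the same section says "We propose to examine as many donors as needed to achieve 100 transplanted liver allografts". Data Collection and Handling merges the two centres' data at the end, so 100 is the right denominator for this analysis.

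No section states an expected event count, a limit on predictors, a selection rule, or a penalised or exact method. The sample-size paragraph addresses a CAP threshold, not this aim.

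Investigational Approach defines the early outcomes: "PNF will be defined as AST>3000, plus INR ≥2.5 or arterial pH ≤7.30 within 7 days from implantation", and "EAD as total bilirubin >10 mg/dL on day 7, INR ≥1.6 on day 7, and ALT or AST >2000 U/L" in the first week. There, death and retransplantation are recorded at 3 to 6 months, depending on the centre. The last row of the event table in the same section carries follow-up to 5 years.

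**The concern.** When a logistic or proportional hazards model has few events per coefficient, maximum-likelihood estimates drift away from zero and vary widely. At the extreme they do not exist, because the predictors separate events from non-events.

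The association of CAP and TE with post-transplant outcome is a listed aim, and the aggregated results are to be published. The Background says that CAP has not been studied in deceased donors before. An exaggerated CAP or TE effect from these models could therefore be carried into later work on donor assessment.

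**Working it through.** **Inputs.** From Data Analysis: N = 100, at least 5 predictors, four event-type outcomes. Not in the documents, and so assumed: event rates, effect sizes and predictor distributions.

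**The plan's own figure.** There is none for this aim. The 5% in the sample-size paragraph is the prevalence of a high CAP value, which is a predictor (100 × 0.05 = 5 livers). The predictive-value statement beside it comes without alpha, power or a null value. Neither can be used here.

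**Step 1: events per predictor** = N × event rate ÷ number of predictors.

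| Assumed event rate | Events | With 5 predictors | With 8 predictors |
|---|---|---|---|
| 3% | 3 | 0.6 | 0.38 |
| 5% | 5 | 1.0 | 0.62 |
| 10% | 10 | 2.0 | 1.25 |
| 20% | 20 | 4.0 | 2.5 |
| 30% | 30 | 6.0 | 3.75 |
| 50% | 50 | 10.0 | 6.25 |

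The binomial probability of fewer than five events in 100 is 82% at a 3% rate, 44% at 5% and 2% at 10%.

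**Step 2: simulated logistic models.** N = 100 and five uncorrelated standard-normal predictors, with log odds ratios per SD of 0.5 (CAP), 0.2, 0.3, 0.3 and 0.3; 2,000 data sets per rate. Overstatement = mean ÷ 0.5 − 1. RMSE = √[(mean − 0.5)² + SD²].

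| Event rate | No usable ML fit | ML mean (SD) | Overstatement | Firth mean (SD) | RMSE, ML vs Firth |
|---|---|---|---|---|---|
| 3% | 21% | 0.68 (1.04) | +36% | 0.45 (0.65) | 1.06 vs 0.65 |
| 5% | 5% | 0.63 (0.84) | +26% | 0.48 (0.57) | 0.85 vs 0.57 |
| 10% | 0% | 0.59 (0.48) | +18% | 0.49 (0.38) | 0.49 vs 0.38 |
| 20% | 0% | 0.55 (0.33) | +10% | 0.49 (0.29) | 0.33 vs 0.29 |

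Two repeats with the same true CAP effect gave ML means of 0.61 and 0.65 at 3%, 0.62 and 0.66 at 5%, 0.59 and 0.60 at 10%, and 0.55 and 0.56 at 20%. One of them also covered 30%, with a mean of 0.54 (+8%). No usable fit occurred in 16% and 19% at 3%, and in 6% and 5% at 5%. The six overstatements at 3% and 5% (+22, +30, +36, +24, +26, +32) average 170 ÷ 6 = 28%.

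The 3% figures are noisy. A repeat with 600 data sets left 504 fits with SD 1.07, so its Monte Carlo margin is 1.96 × 1.07 ÷ √504 = 0.093, or about 19 percentage points.

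**Step 3: other assumptions.** All five log odds ratios 0.405 (odds ratio 1.5), pairwise correlation 0.2, 1,500 data sets per rate.

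| Event rate | No ML estimate | ML bias | Firth bias | ML 95% interval coverage | ML power |
|---|---|---|---|---|---|
| 3% | 24% | +57% | −1% | 99% | 4% |
| 5% | 7% | +33% | −7% | 98% | 7% |
| 10% | 0.1% | +21% | −2% | 95% | 15% |
| 20% | 0% | +12% | −1% | 96% | 28% |
| 30% | 0% | +11% | 0% | 95% | 32% |

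At 3%, the data sets without an estimate include those with no events at all (0.97^100 = 5%). Firth fitting returned an estimate in 94% of data sets at 3% and 99% at 5%.

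**Step 4: what a reader of the results would see.** In the Step 2 setting, among data sets where CAP reached p < 0.05, the mean absolute log odds ratio was 1.46, 1.12 and 0.82 at 5, 10 and 20%. These are 2.9, 2.2 and 1.6 times the true 0.5. Part of this is selection under low power, which penalisation does not cure.

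Proportional hazards models and penalised profile intervals were not simulated.

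**The case against.** **No event rate is given.** This stands. A reader might infer that the documents show these outcomes to be rare, or that the models will have 1 to 4 events per predictor. They do not: that band needs rates of 5 to 20% and exactly five predictors. The ratio would be higher if any single EAD criterion sufficed or if deaths accrued over 5 years, and lower with a longer covariate list. What survives is that with five predictors, ten events each would need a 50% rate.

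**The text is under-specified, not wrong.** It speaks of various analyses, does not say that every predictor enters one model, and does not exclude penalisation; a Firth logistic model is still a logistic model. This stands in part. Ordinary maximum likelihood in a joint model is inferred from the wording and from silence, but it is the natural reading, and nothing steers the analyst elsewhere.

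**The intervals are valid.** This stands. A reader might infer that confidence intervals from these models cannot be relied on. Coverage was 94 to 99% across the simulations, so the intervals are wide, not invalid.

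**Bias is small beside imprecision.** This is true: at 20% it is 0.05 against an SD of 0.33. But Firth fitting reduced both, giving a lower RMSE at every rate.

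**It is a pilot and a secondary aim.** That explains the small N and limits the weight of the point. It is not a reason to leave the fitting method open, and the primary comparison of CAP with biopsy is unaffected.

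**Conclusion.** The point holds for the binary and time-to-event outcomes. With an assumed true log odds ratio of 0.5 per SD, ordinary maximum likelihood overstates the CAP effect by about 10 to 30% at event rates of 20% down to 3%. The exact figure at the lowest rate is uncertain, and under the correlated-predictor assumptions it was larger.

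Non-estimability matters only at about 5% or below: roughly 5% of fits at a 5% rate and 16 to 21% at 3%. A reader might infer that the models generally cannot be fitted; at 10% and above, almost all can. The defect is therefore bias, imprecision and occasional failure to estimate.

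These sizes rest on assumed event rates, effects and predictor distributions, and on logistic models; the extension to proportional hazards is by analogy. The point does not apply to continuous outcomes such as peak ALT and ICU length of stay.

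**What to change.** - In the paragraph on the second secondary aim, state that models for PNF, EAD, retransplantation and death will be fitted by Firth-penalised logistic or Cox regression with profile-likelihood intervals.
- Report the number of events beside each model, and label these models exploratory.
- Reconcile the follow-up periods for death and retransplantation (3 to 6 months against up to 5 years), because they determine the event counts. State also whether the EAD criteria are all required, for the same reason.
- Optionally, close the covariate list and limit it in the sparsest models. Any threshold is a judgement: it trades sparse-data bias against confounding, and no threshold was tested here.

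The cost is SAP wording; the software is standard and no new data are needed. Estimates are shrunk slightly at the lowest event counts (Firth mean 0.45 against 0.5 at a 3% rate). Power is not recovered, so a null result for CAP or TE would remain uninformative.

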The shortage of liver allografts for transplantation causes thousands of patients dying in the liver transplant (LT) waitlist every year. The use of marginal livers is a strategy to close the gap between demand and supply of organs. Steatosis is one of the main parameters determining a marginal liver, and to date there is no method to quantify it in a noninvasive fashion. Controlled-attenuation parameter (CAP) from transient elastography (TE) has successfully been used to evaluate steatosis in patients with liver disease, but its usefulness to address steatosis before LT in organ donors has never been tested. Our primary aim is to determine the accuracy of CAP in the guantification of liver steatosis using liver biopsies as reference. Secondarily we will correlate TE and CAP results, analyze possible associations between CAP/TE and post-LT clinical outcomes, and evaluate the change in CAP after LT. A portable TE device (Fibroscan 530) will be used to quantify the degree of liver steatosis (CAP) and stiffness (TE) in donors before organ procurement. Liver biopsies will be obtained after CAP or at the time of organ procurement. The following post-transplant outcomes will be investigated: primary non-function, early allograft dysfunction, ICU length of stay, retransplantation, and death. A follow up CAP/TE with Fibroscan 502 or 530 will be performed in transplant recipients having an outpatient visit 3-6 months after LT. Based on power calculations the study aims to include as many donors as needed to achieve 100 transplanted liver allografts.

Study Title:	Usefulness of Controlled Attenuation Parameter (CAP) for the assessment of liver steatosis
	in liver donors
PI:	[name], MSc, DSc
Institution:	University of Arkansas for Medical Sciences

Background

Worldwide, there is a shortage of liver allografts to meet the number of patients with end-stage liver disease in need for a liver transplant (LT). As a result of this mismatch between organ demand and supply, about 5000 listed patients do not undergo LT each year and are added to the transplant waiting list pool in the United States.(1) It is estimated that 10-20% of patients in the waiting list will either die or become "too sick to transplant", depending mostly on the degree of liver failure. With increasing waiting list times and LT occurring at higher MELD scores, it is expected that the number of patients dying or becoming too sick to transplant will progressively increase in the forthcoming years.

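### ICU-stay is a planned covariate in the post-transplant outcome models, but it is undefined, and the only ICU variable listed for collection is a post-transplant outcome

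*Combined protocol and SAP*

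**What the plan says.** In Data Analysis, the paragraph on the second secondary aim plans logistic, linear or proportional hazards regression, "depending on the outcome variable of interest (PNF, EAD, retransplantation or death"). Besides CAP and TE, the predictors are to include established donor and recipient predictors of transplant outcome ("i.e. age, MELD, ICU-stay, etc"). Nothing further is said about the ICU term.

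The Investigational Approach gives three data lists:

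- **Donor list**, opening "Before transplantation, the following data will be collected about the donor". It runs from body size and demographics through laboratory values to ischemia times. It has no ICU item.
- **Recipient day-of-transplant list**, with one entry: "Routine labs on the day of transplantation (CBC, chemistry, liver panel, INR"). It has no ICU item.
- **Post-transplant list**, opening "After transplantation, the following liver transplant outcomes will be prospectively documented". It contains "ICU length of stay".

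The opening summary agrees with the third list. It gives the post-transplant outcomes as "primary non-function, early allograft dysfunction, ICU length of stay, retransplantation, and death".

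**The concern.** A covariate in a model relating a donor measurement to a graft outcome should be fixed before the graft can act on it. Age and MELD at transplant meet that condition. Post-transplant ICU stay does not, because a poorly functioning graft can prolong it.

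For retransplantation and death, ICU stay may lie on the path from graft quality to the event. For PNF and EAD, which are defined within the first post-transplant week, it overlaps or follows the event. In either case, adjusting for it can absorb part of the CAP or TE association that the aim is meant to estimate.

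It would also defeat the stated use. The Background presents CAP as a tool for donor assessment before allocation, when post-transplant ICU stay is unknown.

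**Working it through.** The plan gives no figure for this aim (no effect size, event rate or power), so there is none to reproduce. The check is mainly textual.

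**Step 1: can each named predictor be built from listed data?**

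| Predictor | Listed source | Known before or at transplant? |
|---|---|---|
| Donor age | Donor list | Yes |
| Recipient age | Date of birth (Data Collection and Handling) | Yes |
| MELD | Largely derivable from the day-of-transplant labs | Yes |
| ICU-stay | Only match: ICU length of stay, post-transplant list | No |

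ICU-stay is the only named predictor whose sole listed match is measured after transplant.

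**Step 2: how is ICU length of stay classified?** The summary and the Investigational Approach call it an outcome. The outcomes named for the regression models leave it out, and the same paragraph then names ICU-stay as a predictor. That paragraph also allows linear regression, although its four named outcomes are binary or time-to-event. The continuous post-transplant outcomes listed for collection are peak ALT and ICU length of stay, so the plan leaves open whether ICU length of stay is itself modelled.

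**Step 3: timing.** The Investigational Approach defines PNF within 7 days of implantation and EAD by day-7 and first-week values. Retransplantation and death are recorded at 3 to 6 months. A post-transplant ICU stay can therefore overlap or follow PNF and EAD, and can precede the later events. Death can also cut it short.

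**Step 4: direction, by illustration.** Every input here is an assumption, and none comes from the documents. With 400,000 simulated transplants and CAP and baseline severity S as independent standard normals:

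- graft injury G = 0.5·CAP + √(1 − 0.25)·noise;
- post-transplant ICU stay = λ·G + 0.3·S + √(1 − λ² − 0.09)·noise;
- pre-transplant ICU = yes if S + noise > 1;
- logit(event probability) = −2.4 + 0.8·G + 0.4·S, giving an event rate of about 11%.

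Odds ratio per SD of CAP:

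| λ | No ICU term | With pre-transplant ICU | With post-transplant ICU stay |
|---|---|---|---|
| 0 | 1.45 | 1.46 | 1.45 |
| 0.3 | 1.45 | 1.46 | 1.39 |
| 0.6 | 1.46 | 1.46 | 1.27 |
| 0.9 | 1.47 | 1.47 | 1.04 |

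On the log-odds scale the loss is 1 − ln(adjusted)/ln(unadjusted):

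- λ = 0.3: 1 − 0.329/0.372 ≈ 11%
- λ = 0.6: 1 − 0.239/0.378 ≈ 37%
- λ = 0.9: 1 − 0.039/0.385 ≈ 90%

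The loss is nil at λ = 0, and a pre-transplant indicator costs nothing at any λ. The simulation shows direction only. It has ICU stay respond to graft injury but not to the event itself, and it does not let death shorten the stay.

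**The case against.** The strongest reply is that ICU-stay was meant as a baseline variable. It is described as a donor or recipient predictor and stands beside age and MELD, both known before transplant. The outcome carries a different label, ICU length of stay. The Ethics section allows for candidates being inpatients before transplant, so a pre-transplant stay can exist. It would be a legitimate covariate.

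A reader might infer that this reading is impossible because no such field is collected. The documents do not support that. The lists are not exhaustive: Data Analysis plans a sensitivity analysis for donors on vasoactive amines, which no list contains. Absence from a list therefore does not prove that a variable will be unavailable, and it is not certain that the models will adjust for the post-transplant stay.

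A reader might also infer a circular model, with ICU stay on both sides. The outcomes named for these models exclude ICU length of stay. The mention of linear regression makes it possible that it is modelled, but nothing says it would also be a predictor there.

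These replies limit the point without removing it. If the baseline reading is right, the data lists lack a variable the analysis needs. Under Data Collection and Handling, each center gathers its own data and the databases are combined only after the study is completed. An undefined field could then be absent at one center or recorded on a different scale.

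**Conclusion.** The point holds as an either/or. If ICU-stay means the listed variable, the outcome models condition on a consequence of graft function. If it means a pre-transplant stay, the plan does not list it for collection. Both need a change, so this is more than a request for a definition.

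Under the first reading, the likeliest effect is to pull the CAP/TE association toward the null. That assumes poor graft function prolongs ICU stay. The direction is not assured for every outcome, because death shortens the stay and PNF or EAD may come before most of it. A reader might take the simulated losses as an estimate for this trial. They are not: they rest wholly on assumed inputs, and the documents give nothing from which to size the effect.

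The reach is limited to one item in an open-ended example list for the second secondary aim of a self-described pilot. The primary aim, CAP against biopsy steatosis, is untouched, as are the other two secondary aims.

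**What to change.** 1. In Data Analysis, replace ICU-stay with a defined pre-transplant variable, stating whose stay, when and on what scale. One example is recipient in ICU immediately before transplant, yes/no. If the donor's ICU time is meant instead, say so and add it to the donor list.
2. Add the recipient field to the day-of-transplant list in the Investigational Approach, with the same definition at both centers.
3. State that covariates in these models are restricted to those known before or at transplant. Donor variables, age, MELD and ischemia times remain available.
4. Keep post-transplant ICU length of stay as an outcome only, and say whether it is to be modelled, since the summary lists it and the regression paragraph does not.

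The cost is one extra data field at each center and a few lines of wording. Sample size, study procedures and the primary analysis do not change.

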All liver biopsies will be evaluated by two independent liver pathologists blinded to the results of CAP. In all cases, both the snap frozen and formaldehyde liver biopsy specimens will be reviewed and the degree of macrovesicular steatosis graded as per standard recommendations (<5, 5-33%, 34-66%, >66%). Liver pathologists will independently stage fibrosis of liver specimens using the Batts-Ludwig scoring system and the Brunt classification.

Data Analysis

The primary aim is to correlate the CAP results with the degree of hepatic steatosis on the liver biopsy fixed in formaldehyde. Spearman's rho will be used for this analysis. Parallel analyses will be performed with the snap frozen sample, and computerized histomorphometry to determine accuracy of CAP in different possible clinical scenarios. In order to assess whether a threshold value of CAP with a sufficiently high positive predictive value can be defined to obviate the need for a liver biopsy during organ procurement, Receiver Operating Characteristics (ROC) curves will be plotted, and areas under the curve (AUROC) reported as a measure of accuracy of CAP. For this analysis, the magnitude of steatosis in the formaldehyde samples will be dichotomized as \geq 34 or <34% in order to address steatosis as for EDC allografts. A sensitivity analysis using computed histomorphometry results and dichotomizing grading of steatosis as \geq 20 or <20% will be performed in case the prior analysis lacks power, as this degree of steatosis has been found to be associated with poor post-transplant outcomes as well.

Study Title:	Usefulness of Controlled Attenuation Parameter (CAP) for the assessment of liver steatosis
	in liver donors
PI:	[name], MSc, DSc
Institution:	University of Arkansas for Medical Sciences

CAP will be performed with either the M- or XL-probe depending on the skin to liver capsule distance (M-probe if <2.5 cm, and XL-probe when between 2.5 and 3.5 cm) as per manufacturer's recommendations (Echosens, Paris, France).

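### The only quantified support for N = 100 (a CAP threshold with PPV of at least 80%) has no stated criterion and rests on about five flagged livers, where even 5 of 5 has a 95% lower limit of 48%

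*Combined protocol and SAP*

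**What the plan says.** The sample size paragraph in Data Analysis begins with a caveat: "Accurate sample size determination is difficult in this pilot study because the test characteristics are not defined". It then sets the target: "We propose to examine as many donors as needed to achieve 100 transplanted liver allografts". A general remark follows that this will show meaningful differences between high-CAP and low-CAP livers, with no effect size, alpha or power. The one numerical statement comes next: "If the prevalence of unacceptably high CAP value is as low as 5% of the livers", then "the sample size will permit detection of a threshold that has 80% positive predictive value or higher".

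The ROC paragraph, also in Data Analysis, gives the purpose of the threshold. It is to find out whether "a threshold value of CAP with a sufficiently high positive predictive value can be defined to obviate the need for a liver biopsy". The reference positive there is steatosis of at least 34% on the formaldehyde specimen. A second analysis at 20% "will be performed in case the prior analysis lacks power".

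The opening summary puts the sample size more firmly: "Based on power calculations the study aims to include as many donors as needed to achieve 100 transplanted liver allografts". No power calculation appears anywhere in the document.

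**The concern.** A PPV has only the flagged livers as its denominator. If 5% of 100 livers are flagged, the estimate rests on a handful of organs, however many unflagged livers were scanned. The sentence nevertheless presents the sample as sufficient for a PPV of 80% or more, and does not say what would count as detecting it: a point estimate, a test against some null value, or a confidence limit.

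The intended use makes this matter. A threshold meant to replace biopsy needs reasonable assurance that the PPV really is high. A reader who takes the sentence at face value could treat four or five correctly flagged livers as enough. The threshold would also be chosen from the same data, with no validation step described, so the observed PPV will tend to be optimistic.

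**Working it through.** **Inputs.** From the sample size paragraph: N = 100 livers, 5% flagged, target PPV 80% or higher. From Background: a published PPV of 58% for detecting more than 33% steatosis. Alpha, sidedness, power, null PPV and interval width are not stated, so N = 100 cannot be reproduced. Exact one-sample tests, comparisons of flagged with unflagged livers, and precision calculations were tried, and none leads to 100.

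**Number flagged.** 100 × 0.05 = 5. Under Binomial(100, 0.05) the 2.5th to 97.5th percentiles are 1 to 10, and the chance of 4 or fewer is 44%.

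**Precision.** Exact (Clopper–Pearson) limits are used. When all n flagged livers are true positives, the lower limit is 0.025^(1/n) two-sided and 0.05^(1/n) one-sided.

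| True positives / flagged | Two-sided 95% | One-sided 95% lower limit |
|---|---|---|
| 4/5 | 28.4% to 99.5% | 34.3% |
| 5/5 | lower limit 0.025^(1/5) = 47.8% | 0.05^(1/5) = 54.9% |
| 10/10 | lower limit 0.025^(1/10) = 69.2% | 0.05^(1/10) = 74.1% |

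The Wilson lower limit for 5/5 is 56.6%, so the choice of method does not alter the picture.

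**Fewest flagged livers for a lower limit of 80%.**
- Two-sided: 16/16 gives 79.4% and 17/17 gives 80.5%, so at least 17.
- One-sided: 13/13 gives 79.4% and 14/14 gives 80.7%, so at least 14.
- The chance of 17 or more flagged among 100 at 5% is 9.4 × 10⁻⁶, about 0.001%.
- If 5% of all donors examined were flagged, 17 flagged would take 17 / 0.05 = 340 livers.

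**Weaker reading 1: an observed PPV of at least 80%.** With 5 flagged, this means 4 or 5 true positives, with probability 5p⁴(1 − p) + p⁵. The first three true values are assumed for illustration.

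| True PPV | Chance of 4/5 or better |
|---|---|
| 80% | 0.4096 + 0.3277 = 74% |
| 70% | 0.3602 + 0.1681 = 53% |
| 60% | 0.2592 + 0.0778 = 34% |
| 58% (Background) | 0.2376 + 0.0656 = 30% |

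**Weaker reading 2: PPV above a background level.** With 5 flagged and a true PPV of 80%, requiring at least 2/5 tests a null of 5% with one-sided alpha 0.023 and power 99%. Against a null of 20% the rule becomes at least 4/5, with power 74%. Against 58%, no rule exists even at one-sided 0.05, because 5/5 has probability 0.58⁵ = 6.6% under that null.

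**The case against.** The best defence is that the plan never promises a lower confidence limit of 80%. It calls itself a pilot, admits that sizing is difficult, and asks only whether a sufficiently high PPV can be found. If the true PPV were exactly 80%, a two-sided exact lower limit would reach 80% in at most about 2.5% of samples at any N, so that criterion is strict. On a softer reading, such as PPV above background, five flagged livers can give high power.

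This stands in part. The 17 livers are the smallest number at which even a perfect result would reach the limit; they are not a recommended sample size. No number in the plan is miscalculated; the fault is an undefined claim that its own scenario does not support. But the text does not state the softer reading, and rejecting a null of 5% or 20% would not establish 80%.

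It can also be said that 5% is a low case. At 10% flagged, however, 8/10 has a lower limit of 44%. At 20%, 20/20 reaches 83% but 16/20 only 56%. The plan makes its claim at 5%, so it should be judged there.

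More than 100 donors may be scanned. The documents give neither that number nor the flagged share among livers not transplanted. Those livers may also lack the formaldehyde reference: the text of Investigational Approach takes that biopsy after the anastomoses, while its table places it at procurement.

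The fallback at 20% steatosis shows that low power was foreseen. The sentence on 80% PPV does not carry that caution.

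**Conclusion.** The concern holds. At 5% flagged, 100 livers yield about 5 positives. Neither a perfect result on those 5 (lower limit 47.8%) nor one on 10, the top of the likely range (69.2%), establishes a PPV of 80% at conventional confidence. One-sided limits do not change this. The sample can produce an observed PPV of 80% or show that CAP is associated with steatosis; if that was the meaning, the plan should say so.

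The conclusion assumes 100 analysable livers, independent results and a threshold fixed in advance. Choosing the threshold from the data would make matters worse. The 340-liver figure also assumes the same 5% among all donors examined. The primary Spearman analysis is unaffected, which together with the pilot status limits the point to one that should be fixed in the text.

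**What to change.** 1. In the sample size paragraph of Data Analysis, replace the sentence on 5% prevalence and 80% PPV with:

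> With 100 livers and 5% flagged, an observed PPV of 4/5 has an exact 95% CI of 28% to 99.5% and 5/5 has a lower limit of 48%; a two-sided 95% lower limit of 80% needs at least 17 flagged livers, all true positives. Any CAP threshold and its PPV are exploratory because the threshold is chosen from the same data.

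   If the sponsor intended a weaker claim, such as an observed PPV or a test against background prevalence, state it with its null value, alpha and power.

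2. In the ROC paragraph of Data Analysis, state that every PPV and NPV is reported with an exact 95% confidence interval.

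3. In the opening summary, either show the power calculation or remove the reference to one, so that it agrees with the sample size paragraph.

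The cost is one reworded sentence, one added line and one phrase (or the calculation behind it). No patients are added, and the primary analysis and study conduct do not change. The drawback is a less favourable statement of what 100 livers can show.
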